5.1 Screening

Screening will be the same for both the MAD and POC portions of the study.

Screening will take place from Day -28 to Day -1, and assessments may be performed over more than 1 visit. Confirmation that the most current IRB/IEC approved informed consent form (ICF) has been signed must occur before any study-specific screening procedures are performed. Procedures that are part of standard of care are not considered study-specific procedures and may be performed prior to informed consent and used to determine eligibility.

All screened patients will be assigned a unique screening number. The screening number will include a 3-digit site number and a 4-digit sequential number to identify patients from the time of screening. Only eligible patients who are confirmed by central review as meeting the inclusion/exclusion criteria, listed in [Section 4.4](#) and [Section 4.5](#) respectively, will be enrolled in the study. Screened patients who drop out of the clinical study before randomization will be recorded as screen failures. If rescreening occurs, the site will assign a new screening number.

Specific procedures at the screening visit will include:

- Medical history documentation
- Review of inclusion and exclusion criteria

- Patient medical records must contain documentation of SLE diagnosis
- C-SSRS
- Concomitant medication documentation
- Demographics
- Full physical examination
- Vital signs
- Chest x-ray (a prior x-ray can be used if taken within 12 weeks of screening date)
- Laboratory evaluations (non-fasting):
 - Hematology and clinical chemistry
 - Serology (Hepatitis B and C; HIV-1/2 combination)
 - TB test
 - CRP
 - Direct Coomb's test (if indicated for hemolytic anemia)
 - CD4+ count, total IgG and IgM levels, plasma CCI [REDACTED], CCI [REDACTED]
[REDACTED]
 - Serum pregnancy test (WOCBP)
 - FSH (postmenopausal women under age 55 years)
 - Spot urine for protein/creatinine ratio
 - Urinalysis
 - Stool sample
- 12-lead ECG
- SLE-related indices [BILAG-2004 Index, SLEDAI-2K, ACR-28 joint count, CLASI, Physician's Global Assessment (PGA) of disease activity]
- Screening procedures are listed in the Schedule of Assessments ([Table 1](#) and [Table 4](#)), and details are provided in [Section 6](#).

5.1.1 Retesting During Screening Period

A single retesting of laboratory parameters and/or other assessments during the screening period is permitted (in addition to any parameters that require a confirmatory value) only if:

- medically indicated
- there is evidence a laboratory sample was mislabeled, indeterminate, inadequately processed, and/or deteriorated in transit to the central laboratory

Any new result will override the previous result (i.e., the most current result prior to randomization) and is the value by which study inclusion/exclusion will be assessed, as it represents the patient's most current clinical state. This will also apply to patients who are being rescreened.

5.2 Enrollment/Randomization and Day 0 Treatment

Randomization should occur after patient eligibility for enrollment has been confirmed by the central eligibility review. The central eligibility review team has the final decision on patient eligibility and can decide the patient is not eligible for the study based on their review of the eligibility packet.

Prior to randomization, the study site should confirm that the patient still meets inclusion/exclusion criteria (especially SLE disease activity and treatment). The site will obtain a randomization number when registering the patient in interactive web response system (IWRS). All patients will receive BOS161721 or placebo according to the kit number assigned by the IWRS randomization scheme.

After randomization, procedures include:

- PROs: CCI [REDACTED]
- C-SSRS
- Laboratory evaluations (fasting):
 - Hematology and clinical chemistry
 - Direct Coomb's test (if indicated for hemolytic anemia)
 - CD4+ count, total IgG and IgM levels, plasma CCI [REDACTED], plasma CCI [REDACTED] and CCI [REDACTED], whole blood for leukocyte immunophenotype (leukocyte immunophenotype for MAD patients only)
 - ADA
 - pSTAT3 (predose [trough] samples only in phase 1b)
 - CCI [REDACTED]
 - CCI [REDACTED]
 - CCI [REDACTED]
 - See [Table 4](#) and [Table 1](#) for details of PK sampling in the MAD and POC portions
 - Urine pregnancy test will be collected on WOCBP prior to study drug administration
 - Spot urine for protein/creatinine ratio
 - Urinalysis
- Concomitant medication documentation
- Documentation of AEs and SAEs (see [Section 6.2.2.5](#) on SAE reporting requirements)
- Full physical examination
- Vital signs (prior to PK blood draw, predose, and at 1 and 2 hours [\pm 15 minutes] postdose on Day 0)
- 12-lead ECG (prior to PK blood draw)
- SLE-related indices (BILAG-2004 Index, SLEDAI-2K, ACR-28 joint count, CLASI, PGA)

- SLICC/ACR damage index
 - Study drug administration:
 - Administration of BOS161721 or placebo will take place on-site, and is discussed in [Section 7.3](#).
 - Injection site reaction assessment performed at 2 hours postdose
- Procedures on Day 0 are listed in the Schedule of Assessments ([Table 1](#) and [Table 4](#)), and details are provided in [Section 6](#).

All patients who are enrolled, randomized, and receive study drug, or undergo study-specific procedures should re consent with any updated versions of IRB/IEC approved informed consents during study participation as applicable and per institutional guidelines.

5.3 Treatment Period/Follow-Up Visits

The following procedures will be performed as indicated in the Schedule of Assessments ([Table 1](#) and [Table 4](#)). See Schedule of Assessment tables for allowable windows for each visit.

- Targeted physical examination
- Vital signs (prior to PK blood draw)
- Concomitant medication documentation
- Documentation of AEs and SAEs (see [Section 6.2.2.5](#) on SAE reporting requirements)
- PROs: CCI [REDACTED]
- Urine pregnancy tests will be collected on WOCBP prior to study drug administration
- Injection site reaction assessments will be performed predose
- Direct Coomb's test (if indicated for hemolytic anemia)
- Spot urine for protein to creatinine ratio
- Urinalysis
- CCI [REDACTED]
- Plasma CCI [REDACTED]
- PGA, BILAG-2004 Index, SLEDAI-2K, ACR-28 joint count, and the CLASI will be completed
- SLICC/ACR Damage Index will be completed at Day 180
- C-SSRS
- ECGs prior to PK blood draw
- See [Table 4](#) and [Table 1](#) for details of PK sampling in the MAD and POC studies, respectively
- Fasting hematology and chemistry assessments
- The CD4+ count and total IgG and IgM levels

- Plasma CCI [REDACTED] and CCI [REDACTED], ADA, and whole blood for leukocyte immunophenotype (leukocyte immunophenotype for MAD patients only)
- pSTAT3 (predose [trough] samples only phase 1b)
- nAb will be analyzed by central lab if patient is positive for ADA
- CRP
- CCI [REDACTED]

5.4 Safety Follow-Up Visits

Safety follow-up visits will take place at Days 210, 240, and 270. These visits will include the following assessments as indicated in the Schedule of Assessments (Table 1 and Table 4):

- PROs: CCI [REDACTED]
- Documentation of AEs and SAEs (see Section 6.2.2.5 on SAE reporting requirements)
- Injection site reactions
- Targeted physical examination
- Vital signs (prior to PK blood draw)
- Spot urine for protein/creatinine ratio and urinalysis
- Concomitant medication documentation
- BILAG-2004 Index, SLEDAI-2K, ACR-28 joint count, CLASI, and PGA
- Fasting clinical laboratory assessments (hematology and clinical chemistry)
- Direct Coomb's test (if indicated for hemolytic anemia)
- Plasma CCI [REDACTED]
- CCI [REDACTED]
- 12-lead ECG (prior to PK blood draw)
- CRP
- ADA
- CCI [REDACTED]
- Urine pregnancy test
- See Table 1 and Table 4 for details of PK sampling in the MAD and POC portions, respectively

5.5 Premature Discontinuation

While patients are encouraged to complete all study evaluations, they may withdraw from the study at any time and for any reason. Every effort will be made to determine why any patient withdraws from the study prematurely. If the patient is unreachable by telephone, a registered letter, at the minimum, should be sent to the patient requesting him/her to contact the clinic.

All patients who withdraw from the study with an ongoing AE or SAE must be followed until the end of study or until the event is resolved or deemed stable, respectively.

If a patient withdraws prematurely after dosing, an end of treatment (EOT) visit should be performed (Day 180) and a last follow-up visit 90 days after dosing should be scheduled (Day 270). Safety follow-up visit procedures based on the Schedule of Assessments (see [Section 5.4](#)).

Patient participation may be terminated prior to completing the study and the reason recorded as follows:

- AE/SAE
- Protocol deviation
- Lost to follow-up
- Patient withdraws consent at their own request
- Investigator decision
- Decision by the sponsor (other than AE/SAE, protocol deviation, or lost to follow-up)

Withdrawn patients may be replaced after discussion between the Investigator or designee and sponsor.

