2.2 Phase 2 Proof of Concept

OBJECTIVES	ENDPOINTS
Primary	

 • To demonstrate a superior effect of BOS161721 at the chosen dose compared with placebo for response on the SRI-4 	Primary Efficacy Endpoint 
 • The proportion of patients with a SRI-4 response at Day 210 (see Section 6.3.4.1)
Secondary	

 • To demonstrate a superior effect of BOS161721 at the chosen dose compared with placebo for response on clinical indicators of SLE activity, in adult patients with moderately to severely active SLE on limited background standard of care treatment 	Secondary Efficacy Endpoints 
 • The proportion of patients with: 
 - SRI-4 response at each visit - SRI-5 and SRI-6 response at each visit (Section 6.3.4.2) - a sustained reduction from baseline of oral corticosteroid (CS) (≤ 7.5 mg/day and $<$ Day 0 dose) between Day 150 and Day 210 - new or recurrent BILAG flares (≥ 1 qualifying BILAG A or > 1 qualifying BILAG B) through Day 210 - PGA worsening - a BICLA response - a CLASI response

	
 - medication failures • The changes and percent changes from baseline in: 
 - CLASI - PGA - Total number of swollen joints, tender joints, and active joints (swelling and tenderness in the same joint) in the ACR-28 joint count - SLEDAI-2K - SLICC/ACR damage index • Time to medication failure • Group mean percent reduction in CS administration from baseline Day 0 dose through Day 210 in patients receiving ≥ 7.5 mg/day prednisone equivalent at Day 0 • Duration of longest SRI-4 response • Time to first BILAG flare (≥ 1 new or recurrent BILAG A or > 1 new or recurrent BILAG B) relative to baseline through Day 210
--	--

Safety

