3.5 End of Study

End of Study (Individual Patient): A patient is considered at the end of study if he/she has withdrawn, prematurely discontinued, or completed all of the study procedures including the last visit.

End of Study (End of trial): The end of the study is defined as the date of the last visit of the last patient in the study globally, or the date of which the last patient withdraws or discontinues if all prior enrolled patients have already completed/withdrawn.

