5.6 Contingency Plans During the COVID-19 Pandemic

- Safety oversight: In case a patient cannot return to the study site for the scheduled visit, the site staff will contact the patient remotely for safety follow up, for example, via telephone or video conferencing.
- Central Laboratory: In the case there are courier issues that will prevent the protocol-required laboratory specimens to be sent to the study core laboratory, the site should have the safety laboratory specimens ([Table 2: Hematology, Chemistry, and Urinalysis](#)) sent to their local laboratory for analysis and review by the study physician.
- Investigational Product Dosing: In cases when dosing cannot be performed during the protocol-designated windows, the Investigator should discuss each case with the Sponsor to determine whether it is a missed visit or whether the dosing can be performed outside protocol windows (as a protocol deviation). A minimum of 2 weeks must be maintained between consecutive doses. Patients who miss more than 2 doses of the study drug (whether consecutive or not) will be discontinued from the study and will undergo assessments as outlined in [Section 5.5](#) (Premature Discontinuation).

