6.2.1.1 Pregnancy testing

For WOCBP, a serum pregnancy test will be performed at screening. Following a negative serum pregnancy result at screening, appropriate contraception must be commenced or continued and a further negative urine pregnancy test results will then be required at the baseline visit before the patient may receive the investigational product. Urine pregnancy tests will also be routinely repeated at study drug administration visits prior to study drug administration, at the last follow up visit day (Day 270) and additionally whenever 1 menstrual cycle is missed or when potential pregnancy is otherwise suspected. In the case of a positive pregnancy test or confirmed pregnancy, the patient will be discontinued from study drug, an EOT visit should be performed (Day 180), and a last follow-up visit 90 days after last dose should be scheduled (Day 270). Safety follow-up visit procedures (see [Section 5.4](#)) are specified in the Schedule of Assessments (see [Table 1](#) and [Table 4](#)).

See [Section 6.2.2.7.1](#) for information on reporting of pregnancies as AEs/SAEs during the study.

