The patient should return to the investigational site and be evaluated as soon as possible, include laboratory tests, detailed history, and physical assessment. In addition to repeating measurements of AST and ALT, laboratory tests should include albumin, CK, total bilirubin, direct and indirect bilirubin, GGT, prothrombin time (PT)/International Normalized Ratio (INR), and alkaline phosphatase. A detailed history, including relevant information, such as review of ethanol, acetaminophen, recreational drug and supplement consumption, family history, occupational exposure, sexual history, travel history, history of contact with a jaundiced person, surgery, blood transfusion, history of liver or allergic disease, and work exposure, should be collected. Further testing for acute hepatitis A, B, or C infection and liver imaging (e.g., biliary tract) may be warranted. All cases confirmed on repeat testing as meeting the laboratory criteria defined above, with no other cause for liver function test (LFT) abnormalities identified at the time should be considered potential Hy's Law cases irrespective of availability of all the results of the investigations performed to determine etiology of the abnormal LFTs. Such potential Hy's Law cases should be reported as SAEs.

Study drug discontinuation is considered if there is marked serum AST or ALT elevation or evidence of functional impairment (as indicated by rising bilirubin or INR, which represent substantial liver injury) that is related to study drug. Discontinuation of treatment should be considered if:

- ALT or AST > 8 × ULN
- ALT or AST > 5 × ULN for more than 2 weeks

Discontinuation of treatment must occur if:

- ALT or AST > 3 × ULN and (total bilirubin > 2 × ULN or INR > 1.5)
- ALT or AST > 3 × ULN with the appearance of fatigue, nausea, vomiting, right upper quadrant pain or tenderness, fever, rash, and/or eosinophilia (> 5%)

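### The protocol does not separate stopping study drug from leaving the study, and does not explicitly require a Day 210 SRI-4 assessment after either

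*Protocol*

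**What the plan says.** All references are to the current protocol (V7.0).

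- **Endpoint (Section 2.2):** "The proportion of patients with a SRI-4 response at Day 210".
- **Early leavers (Section 5.5):** the section opens with "While patients are encouraged to complete all study evaluations, they may withdraw from the study at any time and for any reason". The first visit on the path is then given: "If a patient withdraws prematurely after dosing, an end of treatment (EOT) visit should be performed (Day 180"). The second and only other visit it names comes later in time: "and a last follow-up visit 90 days after dosing should be scheduled (Day 270"). For procedures it points to Section 5.4, whose visits are Days 210, 240 and 270. Its list of reasons for ending participation includes adverse events, protocol deviation and investigator or sponsor decision, alongside withdrawn consent and loss to follow-up.
- **Missed doses (Section 5.6):** "Patients who miss more than 2 doses of the study drug (whether consecutive or not) will be discontinued from the study", with assessments as in Section 5.5.
- **End of study for a patient (Section 3.5):** "A patient is considered at the end of study if he/she has withdrawn, prematurely discontinued, or completed all of the study procedures".
- **Stopping drug:** for pregnancy (Section 6.2.1.1), "the patient will be discontinued from study drug, an EOT visit should be performed (Day 180"), followed by the same last visit. For the liver criteria (Section 6.2.2.6.3), "Discontinuation of treatment must occur if" introduces the triggers, but no visit path follows. Anaphylaxis (Section 6.2.2.6.1) likewise stops drug without a visit path.
- **Missing data (Section 8.2.3):** LOCF for the primary analysis. Prohibited medication or unallowable corticosteroid use makes the patient a non-responder from that date.

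**The concern.** The primary comparison is response at Day 210 by randomised group. A patient who comes off drug but is still willing to attend can supply that outcome. If the visit path does not ask for it, the data gap comes from the protocol and not from the patient, and the answer for that patient rests on an earlier visit carried forward. Reasons for leaving, such as adverse events, can differ between arms, so the resulting error need not cancel. The SAP can change how a gap is filled, but it cannot recover a Day 210 SLEDAI-2K, BILAG or PGA that was never collected. The remedy therefore belongs in the protocol.

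**Working it through.** **1. The plan's own figure.** Inputs from Section 8.1: 62% versus 33%, 2:1 allocation, 2-sided alpha 0.10, power 80%, Pearson's chi-squared test.

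- Pooled rate = (0.33 + 2 × 0.62)/3 = 0.523.
- Placebo n without continuity correction = [1.645 × √(1.5 × 0.523 × 0.477) + 0.842 × √(0.33 × 0.67 + 0.62 × 0.38/2)]² / 0.29² = 26.6, so 27 placebo and 81 in total.
- With the continuity correction: 32 placebo and 96 in total, which matches the protocol.
- At 32:64 the uncorrected test has 86.2% power (85.8% by exact enumeration), so the stated 80% is conservative for the named test.
- 96/(1 − 14/110) = 110 randomised, which also matches.

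**2. What the allowance covers.** The 14 patients are those never treated or without any post-baseline efficacy measure, so they are outside the FAS. FAS patients who leave later, before Day 210, have no allowance and go to LOCF.

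**3. Does the Section 5.5 path reach Day 210?** Last dose plus 90 days:

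| Last dose (day) | 0 | 30 | 60 | 90 | 120 | 150 | 180 |
|---|---|---|---|---|---|---|---|
| Closing visit (day) | 90 | 120 | 150 | 180 | 210 | 240 | 270 |

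The closing visit falls on Day 210 only when the last dose was on Day 120. The Day 180 and Day 270 labels agree with a 90-day interval only when the last dose was on Day 180. If the labels are read as fixed study days, neither visit is ever Day 210.

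**4. An example under Section 5.6.** A patient misses Days 60, 120 and 180. The third miss triggers study discontinuation at Day 180, 30 days before the primary assessment. The last dose was on Day 150, so the closing visit falls on Day 150 + 90 = Day 240. Neither visit named in Section 5.5 falls on Day 210.

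**5. What fills the gap.** Medication failures are non-responders whether or not they attend. For the others, LOCF takes the latest earlier visit. At best this is the EOT assessment, because the Day 180 column of Table 1 includes SLEDAI-2K, BILAG and PGA. If the EOT visit is held when the patient stops, it may lie months before Day 210.

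**6. Size, for illustration only.** The protocol gives no rate of leaving after the first post-baseline visit. Assume a share m of the 96, equal in both arms. Power uses the formula behind step 1 with uncorrected Pearson: either response rates p(1 − m) at 32:64 (missing counted as non-response), or n(1 − m) at the stated rates (missing excluded).

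| m | Patients (96 × m) | Power, missing as non-response | Power, missing excluded |
|---|---|---|---|
| 0 | 0 | 86.2% | 86.2% |
| 10% | 9.6 | 79.3% | 82.8% |
| 20% | 19.2 | 71.4% | 78.6% |

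Neither column is the protocol's LOCF, whose effect cannot be computed from the document.

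**The case against.** A reader might infer that every patient who stops study drug is taken out of the study. The text does not support that. Section 5.5 is about patients who withdraw. The anaphylaxis and liver sections order only that treatment stop. Section 4.8 speaks of withdrawal from study medication, and Section 3.1.1.2 allows drug to be interrupted. Pregnancy is the only drug-stop case with a visit path. For the rest, the fair charge is silence.

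Nor can one say flatly that Day 210 is never collected. Section 5.5 encourages completion of evaluations and refers to Section 5.4, whose visits include Day 210 with SLEDAI-2K, BILAG and PGA. A last visit does not exclude earlier ones. The EOT visit provides a complete SRI-4 assessment, and medication failures need no imputation. The missed-dose rule needs at least 3 of 7 doses missed, follows case-by-case discussion with the sponsor, and sits in the COVID-19 section, so its reach may be small and is unclear outside that setting.

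Most of this stands and narrows the point. What it does not remove is that encouragement is not a requirement and cannot override the mandated discontinuation in Section 5.6. The reference to Section 5.4 supplies procedures, while Section 5.5 itself names two visits and not Day 210.

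**Conclusion.** The point holds in this limited form. The protocol does not distinguish stopping drug from leaving the study, and it does not explicitly require a Day 210 SRI-4 assessment after either. The firmest limb is Section 5.6, where discontinuation from the study is mandatory even for patients willing to continue, and Section 3.5 then treats them as finished. For drug stoppers in general the defect is ambiguity, not ordered removal.

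The size is unknown. The 10-19 patients and the power losses rest on an assumed 10-20% rate, on every such patient lacking Day 210 data, and on missing-data treatments that are not the protocol's own. They show why the gap is worth closing and do not estimate its effect. The direction of any LOCF bias cannot be told from the document. This does not undermine the sample size, which reproduces; it is an inexpensive improvement that should be made.

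**What to change.** Reconcile Sections 3.5, 5.4, 5.5, 5.6 and 6.2.1.1:

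- Define discontinuing study drug separately from withdrawing consent and from loss to follow-up. Only the latter two end efficacy follow-up.
- State that patients off drug who still consent attend the Day 210 visit already in Table 1, at least for SLEDAI-2K, BILAG, PGA and the corticosteroid record. This includes those reaching the missed-dose limit.
- Resolve the Day 180 and Day 270 labels against the 90-day interval, so that sites know when each visit falls.
- In Section 8.2.3, use the observed Day 210 value in place of LOCF where it exists, with the medication-failure rule still applied. This means that response after stopping drug counts in the primary analysis, and the text should say so.

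Dosing and treatment-stopping rules are not touched. The cost is a short amendment and a few extra visits of an existing type for those who stop early.
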